9.2.4.6 Blood manganese concentration

Blood samples for manganese measurements will be taken on the day of mangoral administration immediately (within 1 hour) prior to dosing and at 24 (± 4), 48 (± 4) and 5 (± 2) days post-dose in all patients. A blood volume of 6 mL will be drawn per time point.

For patients in the PK subgroup (selected from a few sites) additional blood samples for PK assessments will be taken on the day of mangoral administration. Blood samples will be taken on the day of mangoral administration immediately (1 hour pre-dose) and 0.25, 0.5, 1, 2, 3, 4, 6, 8, 12, 24, 48 and 120 hours post-dose.

9.2.4.7 Pregnancy test

A serum pregnancy test will be performed in women of childbearing potential at the local laboratory at screening. A urine or serum pregnancy test will be performed in women of childbearing potential at the local laboratory at baseline, i.e. within 24 hours prior to the administration of mangoral. In the case of pregnancy, the patient is not allowed to enter the study or will be withdrawn from further study participation. The event is to be captured on dedicated CRF page.

9.2.5 Pharmacokinetic parameters

The aim is to evaluate the pharmacokinetics of manganese in a subgroup of patients for whom blood samples were taken after mangoral administration according to a specific sampling schedule. These patients will be selected from a few sites that are able to include these patients and follow PK requirements.

The pharmacokinetic evaluation of manganese will be performed using non-compartmental pharmacokinetic analysis by or under the supervision of the sponsor. Based on the individual blood concentration-time profiles (using the actual sampling times), the pharmacokinetic parameters given in [Table 4](#) will be derived.

Table 4 Pharmacokinetic parameters

Parameter	Description
AUC	Area under the concentration-time curve from zero up to infinity with extrapolation of the terminal phase.
AUC ₀₋₁₂₀	Area under the concentration-time curve from zero until time (120 hours). This parameter may contain an extrapolated portion if t is replaced by a definite time.
AUC ₀₋₂₄	Area under the concentration-time curve from zero until time (24 hours). This parameter may contain an extrapolated portion if t is replaced by a definite time.
C _{max}	Maximum observed concentration after administration.
λ_z	First order rate constant associated with the terminal elimination phase estimated by linear regression of the logarithmic transformed concentration-time plot.
R ² _{adj}	Adjusted coefficient of determination of the terminal regression line.
t _{1/2,z}	The half-life associated with the terminal elimination phase.
t _{max}	Time to attain C _{max} .
Cl _{app}	Total apparent clearance calculated as dose/AUC

LLOQ = lower limit of quantification.

This analysis will also be repeated considering minimum concentration adjusted results (by patient) as below, the new pharmacokinetic parameters will be referred as “adjusted by C_{min}”:

Minimum concentration adjusted = Concentration at timepoint - Minimum concentration

Further the percentages of:

(AUC_{0-24 h} adjusted by C_{min} / AUC_{0-24 h} unadjusted)*100

(C_{max} adjusted by C_{min} / C_{max} unadjusted)*100

9.3 Sample Size Considerations

The primary endpoint analysis consists of two co-primary one-sided t-tests at the conventional one-sided significance level of 0.025. Following the FDA's draft guidance on multiple endpoints in clinical studies, adjustment of the type-I-error is not necessary since both primary variables need to show superiority simultaneously. Nonetheless, this affects the type-II-error. To counteract the inflation of the type-II-error, each test's power is set to 0.9 to achieve a study power of at least $0.9 \times 0.9 = 0.81$.

Effect size

The primary efficacy is based on qualitative parameters. When designing the ASC-Man-P016 study, a conservative approach was applied when calculating the sample size due to uncertainties regarding the assumed treatment effect overall and in patients with HCC lesions in particular, and the impact of using diffusion-weighted imaging (DWI).

The original sample size determination was based on a study investigating a manganese-based contrast agent with T1 / T2-weighted imaging and DWI. Efficacy was evaluated by comparison of unenhanced versus CMRI qualitative score results for “likelihood that a lesion represented a metastasis” on a scale from 1 to 5 [1]. These results were used to derive estimates for mean and standard deviation (SD) and scaled down for the 1 to 4 scale used in this study. Calculating a mean score per patient and averaging readers after rescaling, lead to averages of 2.3 for unenhanced versus 2.6 for CMRI. This is a difference of 0.3 with each sample’s standard deviation of ~1.9, or ~1.5 after rescaling. For estimation of the SD of the samples’ differences, a high correlation (0.8) was assumed, which resulted in SD of differences of 0.95.

Conservatively assuming no effect of the subpopulation of the HCC patients (20% of the study population), the difference in the full population was estimated to $0.3 \times (1-0.2) = 0.24$.

This resulted in a need of 167 patients for the analysis to reach 90% power for each test. With an assumption that only 85% of the image sets would be evaluable (all mangoral-enhanced and unenhanced MRI images) and that no patients would drop out (since the MRI procedures are completed within a few hours for each patient), it was concluded that 197 enrolled patients were required as per the original sample size estimation.

However, since the original sample size estimation, new information relevant to the underlying assumptions of the effect size has become available. This includes a recent re-analysis of the early phase CMC-P004 study [2]. In Study CMC-P004, the MRI images were assessed by 2 investigating radiologists in consensus, who were not blinded to the treatment or the clinical information. A re-read of images from Study CMC-P004 has been performed by utilizing the 3-reader paradigm that is recommended in the guidance for developing medical imaging drugs [3] and is to be used in the present study (Study ASC-Man-P016). The primary objective of the re-read (P004A) was to estimate the diagnostic efficacy of mangoral MRI (combined mangoral-enhanced and unenhanced MRI) and MultiHance® MRI (combined MultiHance®-enhanced and unenhanced MRI) for visualization of focal liver lesions assessed by 3 independent radiologists. The MRI images from Study CMC-P004 were re-assessed according to the procedures described in [Section 9.2.2](#). The preliminary analysis showed that the median effect size (CMRI vs. unenhanced) was 0.74 (data on file).

Study CMC-P004 used a dose of 1600 mg manganese chloride tetrahydrate, which is conservatively assumed to give a 20% higher effect than the 800 mg dose that is used in the ASC-Man-P016 study resulting in an effect size of $0.74 / 1.2 = 0.62$. Further, the effect in the subpopulation with HCC lesions is assumed to be half the effect seen in the population with metastases and potentially constituting up to 30% of the total patient population resulting in the further reduction of effect size to 0.52. The impact of DWI has conservatively been assumed to reduce the contrast effect by further 25%. Taken together, an effect size of $0.52 / 1.25 = 0.42$ is considered relevant and has been used for a new estimation of the sample size.

Sample size

With the effect size of 0.42, 59 evaluable patients are required to achieve 81% power in a single reader test. With the success rule of 2 out of 3, this corresponds to 90% power to meet the co-primary efficacy endpoint. With this smaller sample size, a somewhat larger margin to account for non-evaluable patients

has been applied. In the original calculation 85% evaluable patients of the total population was assumed, but now ~75% of the total population is assumed to be evaluable. With this assumption, at least 80 patients with both unenhanced and mangoral-enhanced MRI will be needed for the primary analysis.

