^bAny simple liver cysts are excluded from primary and secondary variable assessments.

Up to 197 patients with severe renal impairment who are being evaluated for known or suspected focal liver lesions were originally planned to be enrolled at about 60 investigational sites in Europe, Asia, USA and South America. Following a revised sample size estimation (see [Section 9.3](#)), 80 patients were considered sufficient for the analysis of the primary endpoint.

Individual sites are allowed to include study patients with known or suspected HCC; the majority of enrolled patients are considered to have liver metastasis or other common focal liver lesions. Overall, HCC patients are expected to constitute approximately 20% of the total study population.

The schedule of visits and study-related procedures at each visit are presented in the protocol Table 9. Scheduled follow-up visits (FU1, FU2, FU3 and FU4, if required) may be performed as outpatient visits. A subgroup of patients, i.e. patients who underwent brain MRI due to any clinical reason within the last 6 months prior to mangoral-enhanced MRI, for whom previous brain MRI images are available and who have separately consented to this optional brain MRI, shall return to the site for the FU4 visit 7 (+ 2) days after the mangoral-enhanced liver MRI for MRI of the brain.

For the schedule of assessments refer to the protocol Table 9.

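### SAP 9.3 describes a 25% DWI reduction but computes a 20% one, and its 90% power at 59 evaluable patients rests on unstated assumptions

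*SAP*

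**What the plan says.** SAP 9.3 starts from an effect size of 0.74 in a re-read of the early-phase study CMC-P004 and discounts it three times.

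- **Dose.** The earlier study's higher dose is "conservatively assumed to give a 20% higher effect than the 800 mg dose", so 0.74 / 1.2 = 0.62.
- **HCC.** Half the effect in up to 30% of patients, giving 0.52.
- **DWI.** "The impact of DWI has conservatively been assumed to reduce the contrast effect by further 25" per cent, after which "an effect size of $0.52 / 1.25 = 0.42$ is considered relevant".

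The power statement follows: "59 evaluable patients are required to achieve 81% power in a single reader test". Then: "With the success rule of 2 out of 3, this corresponds to 90% power to meet the co-primary efficacy endpoint". On evaluability the SAP moves from 85% to a lower share, "but now ~75% of the total population is assumed to be evaluable", which leads to 80 patients.

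Earlier in the same section each test's "power is set to 0.9 to achieve a study power of at least" 0.9 × 0.9 = 0.81. SAP 13.7.1 specifies one-sided paired t-tests for each reader, with success on both border delineation (BD) and lesion contrast (LC) required from two of three readers.

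**The concern.** The DWI sentence and the DWI calculation disagree. Dividing by 1.25 removes 1 − 1/1.25 = 20%, not 25%. In the dose step the wording (20% higher) and the divisor (1.2) match. The DWI step uses the same kind of divisor but describes a reduction.

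Two further points affect the stated 90% whichever reading was meant.

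- The step from 81% to 90% holds only if the three readers' results are independent. Protocol 6.2.5.1 has every reader assess all images of all patients.
- The SAP does not say whether 0.42 is a raw or a standardised difference, nor which power formula was used.

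The 90% is the written justification for reducing a pivotal trial from 197 patients to 80.

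**Working it through.** **Inputs (SAP 9.3, 13.7.1).** One-sided alpha 0.025; 59 evaluable; effect d = 0.42 as calculated or 0.39 as worded; success on both variables in at least two of three readers.

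**Effect chain.** 0.74 / 1.2 = 0.617. The HCC factor is 0.7 + 0.3 × 0.5 = 0.85, giving 0.524. Then 0.524 / 1.25 = 0.419, or 0.524 × 0.75 = 0.393. From the SAP's rounded 0.52 these are 0.416 (printed as 0.42) and 0.39.

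**Reproducing the SAP.** Treat 0.42 as mean paired difference divided by SD of differences, and use the normal approximation:

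- per test: p = Φ(d√n − 1.960) = Φ(0.42 × 7.681 − 1.960) = Φ(1.266) = 0.897
- both variables in one reader, taken as independent: q = p² = 0.805
- two of three readers, taken as independent: 3q²(1 − q) + q³ = 0.901

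This matches 90 / 81 / 90%. From exactly 0.81, the last step is 3(0.81²)(0.19) + 0.81³ = 0.905. Also 59 / 0.75 = 78.7, which fits 80. Reading 0.42 as a raw difference with the original SD of 0.95 gives a standardised 0.442 and 94.3% for two of three, which does not match. So 59 fits only a standardised 0.42 with the normal approximation.

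**Both readings at 59 evaluable, independence as in the SAP** (t-test power from the noncentral t distribution):

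| Effect | Method | Per test | One reader, BD and LC | Two of three |
|---|---|---|---|---|
| 0.42 | normal | 89.7% | 80.5% | 90.1% |
| 0.42 | paired t | 88.7% | 78.7% | 88.4% |
| 0.39 | normal | 85.0% | 72.2% | 81.1% |
| 0.39 | paired t | 83.8% | 70.2% | 78.7% |

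At 0.39, two-of-three power of 90% needs 69 evaluable (normal) or 71 (t). That is 86% or 89% of 80, against the assumed 75% or so. At 0.42 it needs 59 or 61.

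**Dependence.** Trials were simulated with paired t-tests for three readers and two variables, 20,000 per setting. The correlation across both reader and variable was taken as the product of the two. All correlations are assumptions, because the documents give none. The ranges cover reader correlation 0.3 to 0.7 and BD–LC correlation 0 to 0.95:

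| Evaluable | Effect 0.42 | Effect 0.39 |
|---|---|---|
| 59 | about 82–92% | about 73–86% |
| 68 (85% of 80) | about 89–96% | about 82–92% |

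The low ends combine high reader correlation with independent variables; the high ends are the reverse. At 59 evaluable and 0.42, reader correlation 0.5 with BD–LC correlation 0.8 gives about 88%.

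**The case against.** The strongest reply is that this is only a wording slip. The SAP says 0.42 is the value it used, 0.42 reproduces 59, 81% and 90%, and the dose step divides in the same way. That is plausible, but a reader cannot confirm it from the text, and the two readings differ by 9 to 10 points of power.

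The SAP also holds margins that narrow the gap, and these stand:

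- It discounts for up to 30% HCC, whereas SAP 9.1 says "HCC patients are expected to constitute approximately 20% of the total study population". At 20%, a true 25% DWI cut gives 0.74 / 1.2 × 0.90 × 0.75 = 0.416 and 89.1% (normal) or 87.3% (t) at 59 evaluable.
- At the original 85% evaluability (68 of 80), 0.39 gives 89.8% or 88.3%. If all 80 were evaluable it would give about 95–96%.
- The unrounded 0.393 gives 82.2% or 79.8% at 59, slightly better than 0.39.
- The move from normal to t is small: 90.1% to 88.4% at 0.42. Like for like, the t-test drop is therefore 88% to 79%.

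On correlation, the phrase at least before 0.9 × 0.9 already treats the BD–LC product as a lower bound, so that assumption is on the safe side. It does not cover reader independence, which is the unfavourable one. The two partly cancel, so the true figure could be near 90%.

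Finally, 81% still meets the protocol synopsis's overall study power of 80% on the SAP's own method, though 79% by the planned test falls just short. None of this reconciles the sentence with its calculation.

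**Conclusion.** The concern holds. The words say 25% and the arithmetic applies 20%. If the words are right, two-of-three power at 59 evaluable is 81% on the method that reproduces the SAP (79% by the planned t-test), not 90%. If the arithmetic is right, the planned test gives 88% under independence, and roughly 82–92% over the correlations tried.

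These figures assume that 0.42 and 0.39 are standardised, which is inferred from reproducing 59 patients, and that 59 patients are evaluable. The ranges also depend on assumed correlations. The analysis is not invalidated; what needs correcting is the written power justification. It should be fixed because the reduction in trial size relies on it.

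**What to change.** In SAP 9.3:

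1. Make wording and calculation agree. Either state a further 20% reduction (equivalently, that the effect without DWI is 25% higher) and keep 0.52 / 1.25 = 0.42, or keep 25% and write 0.52 × 0.75 = 0.39.
2. State that the effect size is the mean paired difference divided by the SD of the differences, and compute power with the planned paired t-test.
3. Replace the binomial two-of-three step with a simulation under stated reader and BD–LC correlations. Take these from the CMC-P004 re-read if available; otherwise show a range. That study had 20 patients, so a range is advisable in either case.
4. Report the resulting power in place of 90%, for both 75% and 85% evaluability.

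The cost is a few sentences and a short simulation. If only the wording was wrong, the first item is one phrase. No extra patients are needed; the only downside is that the stated power may fall below 90%.

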9.4 Randomization

No randomization procedure is used, this study is open-label and only has 1 treatment for all patients. However, central read data of the liver from the imaging vendor will be masked to ICON statistics/programming and Ascelia prior to database lock (ICON data management will be unblinded for reconciliation purposes).

10.0 General Statistical Considerations

In general, all continuous measures will be summarized descriptively, including number of available values, minimum, 1st quartile, median, mean, standard deviation, 3rd quartile and maximum. Categorical data will be presented by frequency and percentage. Ordinal ratings may be handled as continuous data.

10.1 Descriptive Statistics

The following descriptive statistics will be calculated for continuous data and for ordered categorical data (ordinal data):

Summary statistics are displayed with the following digits:

Description	Characteristic	Number of decimal places
Count	n	0
Count corresponding to the number of patient for a treatment group	N	0
Mean	Mean	As in source + 1
Standard Deviation	SD	As in source + 2
Minimum, Maximum	Min , Max	As in source
Median	Median	As in source + 1
1 st Quartile / 3 rd Quartile	Q1/Q3	As in source + 1
Percentage relative to N	%	1
Coefficient of Variation (%)	CV (%)	1

+ Number of decimal places will not be displayed where the count is zero, also if percentage is 100% no decimal places will be shown,

For ordered categorical data and nominal data, absolute and relative frequencies (in %) will be calculated:

- Display percentage information only for number of events bigger than zero.
- Percentages will be displayed to 1 decimal place except if it is 100%.

All data will be presented in the patient data listings.

If an output does not include any observations, then the following placeholder will be used: "NO DATA CONTRIBUTED TO THIS TABLE / LISTING / FIGURE".

10.2 Inferential Statistics

Inferential methods will be based on a significance level of 0.05 for 2-sided tests and 0.025 for 1-sided tests. All statistical tests besides the primary efficacy analysis will be interpreted in an exploratory manner.

The testing of efficacy will be done separately for each of the 3 independent readers and will be based on mean scores of BD and LC. For each independent reader, the hypotheses for the superiority of CMRI versus unenhanced MRI will be tested using a 1-sided paired t-test comparing mean score differences between treatment groups, assuming that the differences are normally distributed. As a sensitivity analysis, the non-parametric Wilcoxon signed-rank test will be also performed.

In all statistical tables, p-values will be reported as specified by the statistical program used, at least up to three decimal places. The p-values less than 0.001 will be reported as provided by SAS (e.g. '<0.001').

10.3 Analysis Populations

All patients enrolled in the study (fulfil all inclusion criteria, but none of the exclusion criteria and have been included in the clinical study at Visit 2) will be included in the safety analysis (safety population). The efficacy analysis will be performed in the full analysis set of patients (i.e. who have taken a single dose of the investigational medicinal product) and on a 'per protocol' basis, see definitions below ([Table 5](#)).

Table 5 Definition of analysis populations

Population	Description
Screened Patients	All patients with date of informed consent not missing.
Safety population (SAF) and enrolled patients	All patients enrolled in the study (fulfil all inclusion criteria, but none of the exclusion criteria and have been included in the clinical study at Visit 2).
Dosed Patients	All patients of the safety population who received the IMP.
Full analysis set (FAS)	All patients of the safety population who received the IMP and for whom the primary efficacy variable is assessable, i.e. all unenhanced / enhanced liver MRI images are assessable.
Per protocol set (PPS)	The 'per protocol' set defines the subset of the patients in the FAS without important protocol deviations that could affect the study objectives. All important protocol deviations will be manually reviewed by ICON and Ascelia to agree which to exclude from PPS.
PK population (PKS)	Defines the subset of patients in the FAS who have a blood sample taken at a PK timepoint (0.5, 1, 2, 3, 4, 6, 8 or 12 hours post-dose). These patients will be selected from a few sites that are able to include these patients and follow PK requirements.
Dialysis subgroup population (DSP)	All in the FAS currently on maintenance hemodialysis.
Brain MRI subgroup population (BMSP)	All patients in the FAS with brain MRI performed within 6 months prior to V3 who underwent the optional brain MRI 7 (+2) days after mangoral-enhanced MRI of the liver.

Demographic data and baseline characteristics will be displayed for the SAF, FAS and PPS populations. Efficacy data will be displayed for the FAS and the PPS populations. Safety data will be displayed for the SAF population. Manganese blood concentration data will be displayed for the FAS population, but PK parameters data will only be displayed for the PKS population.

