**PK subgroup:** Pharmacokinetic (PK) evaluations will be performed in a subgroup of patients included in the study. This PK subgroup will consist of 12 patients, including 4 patients currently on maintenance haemodialysis. These patients will be selected from few sites that are able to include these patients and follow PK requirements.

*Inclusion criteria:*

1. Patients who have been fully informed and have personally signed and dated the informed consent
2. Male and female patients 18 years and older
3. Patients who have known or suspected focal liver lesions based on medical history and previous laboratory and/or imaging examinations
4. Patients with severe renal impairment:
  - a. Chronic kidney disease (CKD) (estimated glomerular filtration rate [eGFR]

< 30 mL/min/1.73 m^2) based on medical history and previous laboratory examinations, at least once within the last 3 months prior to the Baseline Visit

OR

b. Acute kidney injury (AKI) with an increase in serum creatinine ≥ 0.3 mg/dL within 48 hours or ≥ 50% within 7 days, prior to the Baseline Visit

5. Female patients who are not of childbearing potential, or female patients who are of childbearing potential but are using highly effective contraception (including hormonal contraceptives, such as combined oral contraceptives, patch, vaginal ring, injectables, and implants, intrauterine device, intrauterine hormone-releasing system, vasectomised partner, and tubal ligation) or practising sexual abstinence (only accepted if this is the usual and preferred lifestyle of the patient), and have a negative urine or serum pregnancy test within 24 hours prior to the administration of contrast agent
6. Sexually active male patients (who are not vasectomised) must be willing to use condoms after administration of mangoral until the last follow-up visit
7. Patients who agree to comply with all study procedures as outlined within the study protocol and informed consent
8. Not applicable

*Exclusion criteria:*

1. Patients with simple liver cysts only
2. Patients who have received any investigational drug or were treated with an investigational device within 6 weeks prior to the Baseline Visit
3. Patients who have received any MRI contrast media within 6 weeks prior to the Baseline Visit or are scheduled to receive any other contrast medium other than mangoral before the last study visit
4. Patients who have previously been enrolled in the study and underwent mangoral-enhanced MRI

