**Table 10 Definition of analysis populations**

Population	Description
Safety population	All patients enrolled in the study (fulfil all inclusion criteria, but none of the exclusion criteria and have been included in the clinical trial at Visit 2).
Full analysis set (FAS)	All patients of the safety population who received the IMP and for whom the primary efficacy variable is assessable, i.e. all unenhanced/enhanced liver MRI images are assessable.
Per-protocol set (PPS)	The per-protocol set defines the subset of the patients in the FAS without major protocol violations, including violations of inclusion/exclusion criteria.
PK population	All patients in the PK subgroup with PK blood samples taken after mangoral administration.
PK dialysis subgroup population (DSP)	All patients in the PK subgroup, currently on maintenance haemodialysis.
Brain MRI subgroup population (BMSP)	All patients with brain MRI performed within 6 months prior to V3 who underwent the optional brain MRI 7 (+ 2) days after mangoral-enhanced MRI of the liver.

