7.1 Changes from Protocol

The planned analysis will be performed according to the study protocol, its amendments and this statistical analysis plan. If there are contradictions between the study protocol or its amendments and this statistical analysis plan, the analysis will be performed according to this analysis plan. Any deviation from the planned analysis according to the study protocol has to be described in the integrated report.

The protocol states that the per protocol set is all patients in the full analysis set without any important protocol deviations. The SAP has been revised to state that only a subset of important deviations will result in patients being excluded from the per protocol set. All important protocol deviations will be manually reviewed by ICON and Ascelia to agree which could have impact on the per protocol set.

The protocol mentions the requirement for adverse drug reactions (defined per protocol as a causal relationship between a medicinal product and an AE to be at least a reasonable possibility) to be collected

and summarized. However, in this study adverse events are only assessed as related or not related so this will be used for the outputs.

The wording and definition of the PK dialysis subgroup population is amended.

The protocol Section 8.1.5 mentions subgroup analysis to be performed on the co-primary variables to be done by status of liver disease, on the subgroup of patients with PK data and also subgroup of patients with brain MRI, this is not included in the SAP as the patient groups are considered to be too small for a meaningful comparison. Subgroup analysis on the co-primary variables by sex will be added. Additionally subgroup analyses is mentioned in the protocol for by lesion diameter on the primary endpoint, this is not planned but different subgroup analyses is planned as described in [Section 13.6.3](#).

The derivations for liver-to-lesion contrast and contrast to noise ratio are amended slightly as described in [Section 11.2.5](#).

QTcB interval (msec) and QTcF interval (msec) were derived in the database but issues were found with these calculations, for this reason these parameters were re-derived in the datasets per the derivations in [Section 11.2.1](#).

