13.7.4 Pharmacokinetic Analysis

The analysis of PK parameters will be performed using the PK Set (PKS). Descriptive and graphical methods will be used to summarize the study results.

The CV and the geometric mean will be additionally included in the descriptive analyses of PK parameters, except for t_{max} . The 2-sided 95% confidence intervals for the geometric means of C_{max} , AUC_{0-t} and AUC will be constructed.

Missing data will be treated as such and will not be imputed or replaced in any way if not specified otherwise.

Individual, mean and overlay blood concentration-time profiles will be plotted on both linear and semi-logarithmic scales. Individual values and descriptive statistics for blood concentration data will be presented by the nominal time point using the Safety Population.

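### SAP Table 5 limits the PK population to patients with assessable liver images, a condition the protocol does not set and SAP 7.1 does not disclose

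*SAP*

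**What the plan says.** **PK population.** Protocol Table 10 defines it as: "All patients in the PK subgroup with PK blood samples taken after mangoral administration". It sets no imaging condition. SAP Table 5 instead starts from the FAS ("Defines the subset of patients in the FAS who have a blood sample taken at a PK timepoint") and lists timepoints from 0.5 to 12 hours. The FAS in that table consists of dosed safety-population patients "for whom the primary efficacy variable is assessable, i.e. all unenhanced / enhanced liver MRI images are assessable".

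**Use of the set.** SAP 10.3 states that "PK parameters data will only be displayed for the PKS population", and SAP 13.7.4 likewise runs the parameter analysis on the PK set.

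**Disclosure.** SAP 7.1 lists several departures from the protocol: the per-protocol set, adverse drug reactions, subgroups, two contrast derivations and QTc. Among the PK-type sets it names one: "The wording and definition of the PK dialysis subgroup population is amended". Where the two documents contradict each other, "the analysis will be performed according to this analysis plan".

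**Size.** Protocol synopsis: "This PK subgroup will consist of 12 patients, including 4 patients currently on maintenance haemodialysis". Pharmacokinetics is a secondary objective (protocol 2.1.2).

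**Concentrations.** SAP 10.3 assigns them to the FAS, while SAP 13.7.4 assigns them to the Safety Population. The version 4.0 entry in the SAP change history records a move from the FAS to the safety set.

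**Safety population.** In protocol 8.1.1 the text says dosed patients, but Table 10 says eligible patients included at Visit 2. The SAP uses the Visit 2 definition in both text and table and adds a separate Dosed Patients set. SAP 7.1 does not mention this choice.

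**The concern.** Whether a liver image can be read says nothing about whether a manganese profile is valid. Nesting the PK set in an image-based efficacy set lets poor image quality remove usable PK data from a small sample that supports a stated objective, including the dialysis patients. The narrower rule is also binding, because the SAP prevails, and a reader of SAP 7.1 would not learn of it. It leaves an anomaly as well: under SAP 13.7.4 a patient's concentrations can be summarised while the parameters derived from them are dropped.

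**Working it through.** **1. Follow one patient through both definitions.** Take a PK-subgroup patient who is dosed and sampled on schedule but has an unassessable liver image.

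| Condition | Protocol Table 10 | SAP Table 5 |
|---|---|---|
| PK sample after dosing | met | met |
| All liver images assessable | not required | required through the FAS; not met |
| PK parameters analysed | yes | no |

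**2. Evaluable fractions in the plan.** Protocol 8.1.14 and SAP 9.3 assume 85% of image sets evaluable: 167/0.85 = 196.5, rounded up to 197, which matches. SAP 9.3 later assumes about 75%: 59/0.75 = 78.7, rounded up to 79, against the stated minimum of 80. The 75% is a planning margin, not an observed image-failure rate. Neither figure is specific to the PK sites.

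**3. Expected loss.** Assume PK patients are evaluable at rate q, independently. Expected number kept = 12q (and 4q for haemodialysis); chance of losing at least one = 1 − q^12 (and 1 − q^4).

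| q | Kept of 12 | Lost of 12 | Lose ≥1 of 12 | Kept of 4 | Lose ≥1 of 4 |
|---|---|---|---|---|---|
| 1.00 | 12 | 0 | 0% | 4 | 0% |
| 0.85 | 10.2 | 1.8 | 86% | 3.4 | 48% |
| 0.75 | 9.0 | 3.0 | 97% | 3.0 | 68% |

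**4. Precision.** SAP 13.7.4 plans two-sided 95% intervals for geometric means. With the SD unchanged, the log-scale half-width in SD units is t(0.975, n−1)/√n:

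- n = 12: 0.635
- n = 11: 0.672, ratio 1.06
- n = 10: 0.715, ratio 1.13
- n = 9: 0.769, ratio 1.21

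**5. What the replacement must still require.** All patients give manganese samples at 24 h, 48 h and day 5 (protocol 6.3.5.3, SAP 9.2.4.6). A rule asking only for some post-dose sample could therefore admit the whole trial population. The samples specific to the PK subgroup are those from 0.25 to 12 h (protocol 6.4.2). SAP Table 5 omits the 0.25 h point.

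**6. Safety denominator (minor).** If post-dose AE percentages were taken over 80 enrolled patients, and 1 to 4 were undosed (an assumption; no number is given), a true 10% would appear as 10% × 79/80 = 9.9% down to 10% × 76/80 = 9.5%.

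**The case against.** The strongest reply is that the running text of SAP 10.3 describes the FAS as patients who took a single dose, with no image condition. SAP 9.2.5 likewise describes the PK patients by their blood samples alone. On that reading the PK set nearly matches the protocol. It is not the better reading: the same sentence of SAP 10.3 refers to Table 5 for definitions, and the image condition there agrees with protocol Table 10 and the protocol synopsis. What stands is that the SAP describes the FAS in two ways, which also needs correcting.

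The size of the loss is also open to challenge. PK patients come from selected sites able to meet the PK requirements and are hospitalised for at least 2 days (protocol 7.1), so trial-wide rates may not apply and the loss could be zero. The PK analysis is descriptive, concentrations are summarised on the Safety Population, and SAP 13.7.4 specifies no separate dialysis summary. All of this stands and limits the consequence; it does not justify the condition.

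On safety, a reader might infer that the SAP leaves the protocol's conflict unresolved. It does not: it adopts the Visit 2 definition throughout and takes precedence. A reader might also infer that undosed patients dilute every post-dose AE percentage. SAP 13.8.1 sets its frequent-event threshold on dosed patients and does not state the other denominators, and the table shells are a separate document. Nor is it shown that dosed patients later found ineligible would be lost: the Visit 2 wording, read literally, leaves them out, but SAP 10.4 and the protocol's per-protocol rule treat such violations as deviations.

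**Conclusion.** The point holds for the PK population. SAP Table 5 adds an image condition that protocol Table 10 lacks, SAP 7.1 does not disclose it, and the SAP governs. Only the derived PK parameters are exposed. The expected loss is 0 to about 3 of 12 patients over an evaluable range of 100% to 75%, with log-scale intervals up to 21% wider at n = 9. These figures assume that trial-wide planning rates apply to the PK sites and that patients are independent; the documents show no actual loss. The primary test is not affected. It should be fixed because the correction is cheap and the sample small.

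The safety-population point is one of disclosure only: SAP 7.1 should state a choice that the SAP has already made.

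**What to change.** **PK, in the SAP:**

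- Define the PK set as dosed PK-subgroup patients with at least one sample at a PK-subgroup timepoint (0.25 to 12 h post-dose), without the FAS condition.
- Record the definition in SAP 7.1.
- Correct the SAP 10.3 sentence on concentrations so that it names the Safety Population, as SAP 13.7.4 and the version 4.0 log do.
- Align the running-text description of the FAS in SAP 10.3 with Table 5.

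**Safety, disclosure only:** say in SAP 7.1 that the Visit 2 definition was chosen over the protocol's text. State that post-dose AE percentages use the existing Dosed Patients set as denominator, in line with the SAP 13.8.1 threshold. Do not redefine membership of the safety set or the FAS by a SAP edit alone. The FAS is a subset of the safety set, and protocol 8.1.11 requires a protocol amendment for any deviation that affects the confirmatory analysis.

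**Cost:** SAP wording, the SAP 7.1 entries and one population flag before database lock. No new data and no change to the sample size.
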